## Study Visits – C4D1, C4D15, C5D1, C7D1, C7D15, and C8D1 When Dose Increased to 25 mg/m² of Miransertib

Cycles 4 and 7 - Day 1 (± 5 days) (dose increase to 25 mg/m²)	Cycles 4 and 7 - Day 15 (± 3 days) (dose increase to 25 mg/m² on C4D1 or C7D1 respectively)	Cycles 5 and 8 - Day 1 (± 5 days) (dose increase to 25 mg/m  on C4D1 or C7D1 respectively)

 
Physical examination, including skin
 
Vital signs (height, weight, temperature, blood pressure, respiration rate, and heart rate)
 
Calculate BSA using the DuBois formula
 
12-lead ECG, predose
 
Fasting Clinical Blood Tests
 
Urinalysis
 
Fibrinogen and D-dimers
 
Where relevant, additional functional test(s) to evaluate individual participant disease status – frequency as per standard of care
 
Dispense miransertib
 
Collect and count returned miransertib
 
Record concomitant medication
 
	
 
Physical examination, including skin
 
Vital signs (temperature, blood pressure, respiration rate, and heart rate)
 
Blood sample for insulin/glucose
 
Record concomitant medication
 
Assess AEs
 
	
 
Physical examination, including skin
 
Vital signs (height, weight, temperature, blood pressure, respiration rate, and heart rate)
 
Calculate BSA using the DuBois formula
 
12-lead ECG, predose
 
Fasting Clinical Blood Tests
 
Blood samples for PK
 
Where relevant, additional functional test(s) to evaluate individual participant disease status, frequency as per standard of care
 
Dispense miransertib
 
Collect and count returned miransertib
 
Record concomitant medication
 
Assess AEs
 

Assess AEs		

## **Study Visits – After 12 Cycles of Treatment**

Cycles* 16, 19, 22, 28, 31, 34, 40, 43 and 46 - Day 1 (± 5 days)	Cycles* 25 and 37 - Day 1 (± 5 days)

 
Physical examination, including skin
 
Vital signs (height, weight, temperature, blood pressure, respiration rate, and heart rate)
 
Calculate BSA using the DuBois formula
 
12-lead ECG, predose, if clinically indicated or required per standard of care
 
Fasting Clinical Blood Tests Urinalysis
 
Urinalysis
 
Dispense miransertib
 
Collect and count returned miransertib
 
Record concomitant medication
 
	
 
Physical examination, including skin
 
Vital signs (height, weight, temperature, blood pressure, respiration rate, and heart rate)
 
Calculate BSA using the DuBois formula
 
12-lead ECG, predose
 
Fasting Clinical Blood Tests
 
Urinalysis
 
Dispense miransertib
 
Collect and count returned miransertib
 
Record concomitant medication
 

• Assess AEs	Assess AEs

\*After the initial 12 months of treatment, the participant may continue receiving treatment and will be seen at the study site once every 3 months per the schedule outlined above.

## Study Visits - End of Treatment, 30 Day Safety Follow-Up

	End of treatment/EOT* (within 7 days of decision to permanently discontinue)	30-day Safety Follow-up* (30+ days after last dose)
•	Physical examination, including skin	Record concomitant medication
•	Vital signs (height, weight, temperature, blood pressure, respiration rate, and heart rate)	• Assess AEs
•	12-lead ECG	
•	Fasting Clinical Blood Tests Urinalysis	
•	Serum pregnancy test, if applicable	
•	Collect and count returned miransertib	
•	Record concomitant medication	
•	Assess AEs	

\* EOT visit, 30-day safety follow-up and 3-cycle safety follow-up assessments to be performed whenever the participant permanently discontinues miransertib (whether during the first 12 cycles or after the first 12 cycles)

75

1 INTRODUCTION

This document details the planned statistical analyses for the ArQule, Inc., (a wholly owned subsidiary of Merck Sharp and Dohme, a subsidiary of Merck & Co., Inc.), protocol "MK-7075-002/ARQ 092-103" study titled "A Phase 1/2 Study of ARQ 092 (Miransertib) in Subjects with PIK3CA-related Overgrowth Spectrum and Proteus Syndrome".

2 STUDY DESIGN

This is an open label, multi-center Phase 1/2 study of oral miransertib administered daily to patients with phosphatidylinositol-4,5-bisphosphate 3-kinase, catalytic subunit alpha (PIK3CA)-related Overgrowth Spectrum (PROS) and Proteus Syndrome (PS). This is a two-part study (Part A and Part B) that will be conducted at approximately 20 sites globally.

Part A includes all participants enrolled in the study prior to Protocol Amendment 6. Part A was designed to enroll 25 to 40 participants with PROS and PS. These participants will continue treatment according to the schedule of drug administration/assessments they have been on at the time of the amendment 6 approval.

Part B includes all participants enrolled under Protocol Amendment 6 or higher. Part B will enroll approximately 65 participants with clinical diagnosis of PROS or PS with documented somatic PIK3CA or v-Akt murine thymoma viral oncogene homolog (AKT1) mutations. Part B is comprised of four cohorts.

- Cohort 1 will enroll 20 participants with PROS with a measurable lesion by the studystandardized volumetric magnetic resonance imaging (MRI).
- Cohort 2 will enroll 10 participants with PS with measurable cerebriform connective tissue nevus (CCTN) and pre-CCTN lesional area by the study-standardized photography.
- Cohort 3 will enroll approximately 25 PROS or PS patients who do not meet the eligibility criteria for enrollment in Cohort 1 or Cohort 2.
- Cohort 4 will enroll participants previously treated with miransertib or currently receiving miransertib under Compassionate Use/Expanded Access.

Template: WCT-TP-ST-005-005 Effective Date: 15-Apr-2016 Page 5 of 24 Confidential

Cohorts 1 and 2 were originally designed to determine the response rate of miransertib in a selected participant population, as measured by a change in target lesion size from baseline, using blinded independent central imaging review: volumetric MRI in PROS or cerebriform connective tissue nevus (CCTN) photography in PS.

In Part B (except Cohort 4), participants will receive miransertib at the 15 mg/m² qd dose level during the first 3 cycles (a cycle of therapy is considered to 28 days). The dose will be increased to 25 mg/m² qd provided no clinically significant drug-related toxicity is observed. Participants who experienced miransertib-related toxicity or are unable to tolerate study medication during the first 3 cycles may be treated at lower doses.

Participants enrolled in Cohort 4 will continue treatment at the dose they were on at the time of enrollment, but their dose should not exceed the 25 mg/m².

Participants will stay on treatment for up to 48 cycles.

The study data and endpoints underwent an internal review by the Sponsor in 2020. It was concluded that the current data from this study would not be sufficient to establish efficacy for either the PROS or PS patients. As a consequence, Protocol Amendment 7 was written to remove all efficacy assessments, including the volumetric MRIs for the PROS patients, the CCTN photography for the PS patients, as well as to remove the functional assessments, among others.

2.1 Study objectives

2.1.1 Primary Objective

The primary study objective for both Part A and Part B is to describe the safety and tolerability of miransertib in patients with PROS and PS.

2.2 Endpoints

2.2.1 Part A and Part B Endpoints

Template: WCT-TP-ST-005-005 Page 6 of 24 Effective Date: 15-Apr-2016 Confidential

Under Protocol Amendment 7, the endpoints for Part A and Part B have been combined to assess the safety and tolerability of miransertib in participants with PROS and PS based on the frequency, duration, and severity of AEs from the first dose of the drug through 90 days after the last dose of the drug.

2.3 Sample size

Part A:

Enrollment in Part A was stopped upon approval of Protocol Amendment 6. 25 to 40 participants were planned to be enrolled.

Part B: Cohorts 1 and 2

Part B of this study was originally designed to determine the efficacy in PROS and PS patients treated with a daily dose of miransertib. The primary endpoint for Cohort 1 and Cohort 2 was response rate as assessed by blinded reviewers (with adjudication) using protocol response criteria. The sample size was justified based on the precision of a 95% confidence interval (CI) on the response rate. To exclude a clinically irrelevant response rate of 5%, the lower limit of the 95% CI should be higher than 5%.

- Cohort 1, PROS: A sample size of n=20 participants will provide a two-sided exact Clopper-Pearson 95% CI of (6%, 44%) on an observed response rate of 30%.
- Cohort 2, PS: A sample size of n=10 participants will provide a two-sided exact Clopper-Pearson 95% CI of (7%, 65%) on an observed response rate of 30%.

With Protocol Amendment 7, efficacy assessments will no longer be collected, and the primary objective of the study is the evaluation of safety and tolerability of miransertib.

Part B: Cohorts 3 and 4

Approximately 25 and 10 patients will be enrolled in Cohorts 3 and 4, respectively.

3 RANDOMIZATION

This is an open label study, with all participants receiving miransertib, so randomization is not applicable.

Template: WCT-TP-ST-005-005 Page 7 of 24 Effective Date: 15-Apr-2016 Confidential

4 PLANNED ANALYSES

No statistical analysis plan (SAP) prepared in advance of the data can be absolutely definitive and the final clinical study report (CSR) may contain additional tables or statistical tests if warranted by the data obtained. The justification for any such additional analyses will be fully documented in the final CSR.

4.1 Analysis Sets

Participants excluded from the analysis sets and the reason for their exclusion will be listed.

4.1.1 Screened Population

The Screened Population includes all participants who were screened and who signed informed consent.

4.1.2 Safety Population

The Safety Population includes all participants who received at least one dose of study medication.

4.2 Derived Data

This section describes the derivations required for statistical analysis. Unless otherwise stated, variables derived in the source data will not be re-calculated.

4.2.1 Race

Where more than one race category has been selected for a participant, these race categories will be combined into a single category labeled "Multiple Race" in the summary tables. The listings will reflect the original selected categories.

4.2.2 Baseline

Unless otherwise defined, baseline is defined as the last non-missing value (either scheduled, unscheduled or repeat) before the participant receives the first dose of miransertib.

Template: WCT-TP-ST-005-005

Page 8 of 24

Effective Date: 15-Apr-2016

Confidential

4.2.3 Duration/Study day/Time

Study day will be calculated as the number of days from first dose of miransertib.

- date of event date of first dose of miransertib + 1, for events on or after first dose
- date of event date of first dose of miransertib, for events before first dose.

4.3 Conventions for Missing and Partial Dates

All rules explained below for partial/missing dates will be followed unless contradicted by any other data recorded on the electronic Case Report Form (eCRF).

All dates presented in the individual participant listings will be as recorded on the eCRF (i.e., not completed as per the below rules).

4.3.1 Missing/Partial Start/Stop Date of Adverse Events and Concomitant Medications

Missing and partial start and stop date will be imputed for analysis purposes as follows.

Partial or missing stop date will be imputed as follows:

If the stop date is completely missing and the event has resolved or the participant has stopped taking the concomitant medication, the stop date will be imputed as the date of the participant's last clinic visit in the study.

- If only the year is known, the stop date will be imputed as "31-Dec" of that year or as the date of the participant's last clinic visit in the study if in the same year.
- If the month and year are known, the stop date will be imputed as the last day of that month unless the stop date corresponds to the same month as the participant's last clinic visit in which case the date of participant's last clinic visit in the study will be used instead.

Missing start date will be imputed as follows:

• If the stop date occurs on or after the start of study drug or the event/concomitant medication is ongoing, the start date will be imputed as the date of the first dose of study drug.

Template: WCT-TP-ST-005-005 Page 9 of 24 Effective Date: 15-Apr-2016 Confidential

• If the stop date occurs before the start of study drug, the start date of the event/concomitant medication will be imputed as the participant's screening date or the stop date of the event/concomitant medication whichever the earlier.

Partial start date (year present, but month and day missing)

- If the stop date occurs on or after the start of study drug or the event/concomitant medication is ongoing, and the year is the same as the year of first dosing the start date will be imputed as "01-Jan" of the same year or the date of the first dose of study drug whichever is latest. If the year is different from the year of first dosing "01-Jan" will be used.
- If the stop date occurs before the start of study drug, the start date of the event/concomitant medication will be imputed as the "01-Jan" of the same year.

Partial start date (month and year present, but day missing)

- If the stop date occurs on or after the start of study drug or the event/concomitant medication is ongoing, the start date will be imputed as the first day of the same month and year unless this partial start date is in same month as the first dose of study drug in which case the date of first dose of study drug will be used.
- If the stop date occurs before the start of study drug, the start date will be imputed as the first day of the month and year of the partial stop date.

4.3.2 Missing Last Dates of Study Drug Dosing

If the date of last dose of study drug is completely missing, then the date of last dose of study drug will be taken for analysis purposes as the date when the participant would have run out of study drug assuming full compliance from the date the study drug was last dispensed or the date of participant's last clinic visit in the study or early withdrawal or death whichever the earlier.

If only the month and year of the last dose was recorded, then the date of last dosing will be taken for analysis purposes as the date the participant would have run out of study drug assuming full compliance from the date the study drug was last dispensed, the last day of the month of the recorded last dose or the date of participant's last clinic visit in the study or early withdrawal or death whichever the earlier.

4.3.3 Missing Diagnosis Dates

Template: WCT-TP-ST-005-005 Page 10 of 24 Effective Date: 15-Apr-2016 Confidential

If the month and year are present but the day is missing, the diagnosis date will be set to first day of the relevant month. If only the year is recorded the diagnosis date will be set as "01-Jan" for that year.

4.3.4 Exposure to Study Drug

Exposure to miransertib will be calculated as follows: date of last dosing minus the first day of dosing + 1. The exposure calculation will not take into account breaks in therapy.

4.3.5 Inexact Values

In the case where a laboratory variable is recorded as "> x", " \geq x", "< x" or " \leq x", a value of x will be taken for analysis purposes.

4.3.6 Electrocardiogram Data

For electrocardiogram (ECG) data recorded on continuous scales, if more than one value is recorded at a time point, the mean value rounded to the integer will be presented. For overall interpretation if more than one value is recorded, the most severe (worst case) of the respective readings will be taken.

4.3.7 Unscheduled Visits

Only scheduled post-baseline laboratory, vital signs, and ECG values will be tabulated. Post-baseline repeat/unscheduled assessments will be disregarded, although these post-baseline assessments will be listed in the relevant appendices to the CSR.

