4.17 Laboratory Data

Template: WCT-TP-ST-005-005 Page 18 of 24 Effective Date: 15-Apr-2016 Confidential

Descriptive statistics of the observed values and change from baseline (continuous data) will be presented by Part, Cohort, and treatment cycle for the following laboratory parameters:

- Hematology: complete blood count (CBC) including hemoglobin, hematocrit, white blood cell count with 5-part differential, red blood cell, platelet, and reticulocyte count
- Hemoglobin A1c (HbA1c)
- Coagulation tests (screening only): prothrombin time (PT), partial thromboplastin time (PTT), international normalized ratio (INR), D-dimer, and fibrinogen
- Blood chemistry: alkaline phosphatase, bicarbonate, calcium, phosphorus, magnesium, albumin, glucose, serum creatinine, and insulin
- Liver function tests: aspartate aminotransferase (AST), alanine aminotransferase (ALT), lactate dehydrogenase (LDH), alkaline phosphatase, total and direct bilirubin, uric acid, total protein, and blood urea nitrogen (BUN)
- Electrolytes: sodium, potassium, and chloride
- Lipids: cholesterol, high-density lipoprotein (HDL), low-density lipoprotein (LDL), and triglycerides

Each blood chemistry and liver function test parameter will be classed as below, within, or above normal range, based on ranges supplied by the laboratory used. Shift tables from baseline to the minimum post-baseline value and separately to the maximum post-baseline value will be presented by Part, Cohort, and overall.

The incidence of post-baseline ALT, AST, ALP, and total bilirubin values meeting CTCAE criteria will be summarized by Part, Cohort, and overall. Refer to Appendix 1 of this SAP for CTCAE definitions for these parameters. Additionally, the incidence of participants meeting Hy's law criteria will be summarized. Hy's law criteria are defined as follows:

- ALT ≥5xULN or
- ALP ≥2xULN or
- ALT ≥3xULN and total bilirubin ≥2xULN

For the third criterion which requires both an elevated ALT and elevated total bilirubin value, both lab values must be elevated at the same visit in order to be counted.

Template: WCT-TP-ST-005-005 Page 19 of 24 Effective Date: 15-Apr-2016 Confidential

The following laboratory parameters will be listed only:

- Serum pregnancy test for female patients of childbearing potential, if applicable
- Routine urinalysis: dipstick and microscopy including protein, glucose, and blood; pH, and specific gravity

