A listing of all post-baseline clinically significant ALT, AST, ALP, or total bilirubin measurements, defined as measurements meeting ≥CTCAE grade 3 criteria, recorded throughout the treatment period will be presented.

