9 APPENDIX 1: CTCAE GRADES FOR SELECT LABORATORY PARAMETERS

Parameter	Unit	Definition	Grade 1	Grade 2	Grade 3	Grade 4
ALT	U/L	High	>ULN-3.0xULN if baseline was normal; 1.5-3.0x baseline if baseline was abnormal	baseline was normal; >3.0-5.0x baseline if	baseline was	>20.0xULN if baseline was normal; >20.0x baseline if baseline was abnormal
AST	U/L	High	baseline was normal;	>3.0-5.0x baseline if	baseline was	>20.0xULN if baseline was normal; >20.0x baseline if baseline was abnormal
Alkaline phosphatase	U/L	High	>ULN-2.5xULN if baseline was normal; 2.0-2.5x baseline if baseline was abnormal	baseline was normal; >2.5-5.0x baseline if	baseline was	>20.0xULN if baseline was normal; >20.0x baseline if baseline was abnormal
Total bilirubin	mg/dL	High		>1.5-3.0xULN if baseline was normal; >1.5-3.0x baseline if	baseline was	>10.0xULN if baseline was normal; >10.0x baseline if baseline was abnormal

Template: WCT-TP-ST-005-005 Effective Date: 15-Apr-2016 Page 23 of 24 Confidential

Issue Date: 09May2022

Parameter	Unit	Definition	Grade 1		Grade 2		Grade 3	Grade 4
			baseline v abnormal	was	baseline abnormal	was	baseline if baseline was abnormal	

ULN=Upper limit of normal

Values in table are based on CTCAE v5.0.

Template: WCT-TP-ST-005-005

Effective Date: 15-Apr-2016

Page 24 of 24

Confidential

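### SAP 4.3.7 bars unscheduled laboratory values from every table, so the worst-value shift tables, liver CTCAE incidence and Hy's law count can be too low

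*SAP*

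**What the plan says.** SAP section 4.3.7 sets a general rule: "Only scheduled post-baseline laboratory, vital signs, and ECG values will be tabulated". It continues: "Post-baseline repeat/unscheduled assessments will be disregarded, although these post-baseline assessments will be listed in the relevant appendices to the CSR".

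SAP section 4.17 then plans three laboratory outputs that summarise the whole post-baseline period rather than a visit:

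- For blood chemistry and liver function tests: "Shift tables from baseline to the minimum post-baseline value and separately to the maximum post-baseline value will be presented".
- "The incidence of post-baseline ALT, AST, ALP, and total bilirubin values meeting CTCAE criteria will be summarized", using the grade cut-offs in Appendix 1.
- The number of participants meeting any of the SAP's Hy's law criteria: ALT at least 5xULN, or ALP at least 2xULN, or ALT at least 3xULN with total bilirubin at least 2xULN. For the last of these, "both lab values must be elevated at the same visit in order to be counted".

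Section 4.17 states no exception to 4.3.7. SAP section 7, which records departures from the protocol analysis, adds none; its only specific change concerns compliance. Baseline follows a different rule. Section 4.2.2 takes "the last non-missing value (either scheduled, unscheduled or repeat) before the participant receives the first dose of miransertib".

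The protocol foresees laboratory tests outside the visit schedule. Section 5.3 allows them between visits to assess an adverse event, if need be near the participant's home. Section 7 allows them whenever clinically indicated.

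**The concern.** A by-visit mean or change from baseline needs one value per participant per planned time point, so leaving out extra samples is sensible there. Those tables are not in question. A maximum, a minimum or an ever-met incidence asks something else: what was the worst value seen? Leaving out samples then removes part of the answer.

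The samples removed are not a random subset. Many are drawn because an event was suspected or a previous result needed checking. The shift tables are also lopsided, since the baseline category may come from an unscheduled sample and the worst post-baseline category may not.

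Safety and tolerability is the study's only objective (SAP 2.1.1). Protocol section 6.9 names transaminase elevation among the risks to monitor. A reader who sees a low rate of Grade 3 ALT, or no Hy's law cases, would take it as a statement about all the laboratory data, and under 4.3.7 it would not be.

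**Working it through.** The plan gives no figure on this point to reproduce. The check has four parts.

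**1. Direction.** Let S be a participant's scheduled post-baseline values and A all post-baseline values, so S is contained in A. Then max(S) ≤ max(A) and min(S) ≥ min(A), and any threshold criterion met in S is also met in A. Under the scheduled-only rule the tabulated maximum can only stay the same or fall. The minimum can only stay the same or rise. Counts of participants at or above a given grade, or meeting a Hy's law criterion, can only stay the same or fall.

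**2. Worked case (assumed values).** Take a participant with normal baseline ALT, highest scheduled ALT 2.5xULN, and one unscheduled ALT of 6xULN.

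- Scheduled only: 2.5xULN lies in the Appendix 1 Grade 1 band, ">ULN-3.0xULN if baseline was normal". The criterion ALT ≥5xULN is not met.
- All values: 6xULN is above the 5.0 upper bound of Grade 2 and below the Grade 4 start of >20.0xULN, so Grade 3. Since 6 ≥ 5, the criterion is met.

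Counted by maximum grade, the scheduled-only rule gives Grade 3 one fewer, Grade 1 one more, any grade unchanged, and the Hy's law count one fewer.

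**3. Effect of one participant = 1/N.** This uses the planned sizes in SAP sections 2 and 2.3 and assumes that all are dosed and have a post-baseline value.

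| Group | N | 1/N, percentage points |
|---|---|---|
| Cohort 2 or Cohort 4 | 10 | 10.0 |
| Cohort 1 | 20 | 5.0 |
| Cohort 3 | 25 | 4.0 |
| Part B | 65 | 1.5 |
| Parts A and B | 25 to 40, plus 65 = 90 to 105 | 1.1 to 1.0 |

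**4. Can a scheduled draw miss an excursion?** Protocol Tables 3 and 4, with 28-day cycles, give these nominal gaps between post-baseline blood tests:

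- Cohorts 1 to 3: 28 days (C2 to C5), 56 days (C5 to C13), then 84 days.
- Cohort 4: 84 days, with the first on-treatment draw at C4, Day 3 × 28 + 1 = 85.

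The documents give no duration for a laboratory excursion, so this is an illustration. If an excursion lasts D days and starts at random within a gap of G days, the chance that a scheduled draw falls inside it is min(1, D/G).

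| D (assumed) | G = 28 | G = 56 | G = 84 |
|---|---|---|---|
| 7 days | 25% | 12.5% | 8.3% |
| 14 days | 50% | 25% | 16.7% |
| 21 days | 75% | 37.5% | 25% |
| 42 days | 100% | 75% | 50% |

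For scale, 21 days is the period against which protocol section 6.5 judges recovery during a dose hold. Suppose five participants each had one 21-day excursion in an 84-day gap. Scheduled draws would fall inside 5 × 0.25 = 1.25 of them on average, and inside none with probability 0.75^5 = 0.237. The rest could reach the tables only through unscheduled samples.

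**The case against.** The strongest reply is that nothing is lost.

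- **AE reporting.** Protocol section 7.1.1 counts an abnormal laboratory finding as a possible adverse event. Section 7.2 has investigators review laboratory results at scheduled and nonscheduled visits. An unscheduled ALT of 6xULN would ordinarily be reported, graded and shown in the TEAE table by maximum toxicity (SAP 4.16). This largely stands as reassurance about the primary endpoint. It depends on the investigator's judgment, though, and does not correct a laboratory incidence computed from measured values.
- **Listings.** Protocol section 9.4 promises listings of laboratory results with CTCAE grades. SAP 4.17 adds "A listing of all post-baseline clinically significant ALT, AST, ALP, or total bilirubin measurements" of Grade 3 or higher, which would show the ALT example. A listing is not an incidence, however, and the Grade 3 limit misses some Hy's law cases. With normal baselines, ALT 4xULN with bilirubin 2.5xULN is Grade 2 on both, and ALP 2.2xULN is Grade 1, yet both patterns meet the SAP's criteria.
- **Another reading.** Section 4.17 speaks of post-baseline values without the word scheduled, so a programmer might treat it as overriding 4.3.7. But 4.3.7 is the explicit text and covers every tabulated laboratory value. If an override was meant, it has to be written.
- **Baseline contrast.** Choosing a baseline and setting a tabulation convention are different purposes, so the difference alone is not an error. That is fair. It shows only that the SAP names unscheduled values when it wants them used.
- **Percentages.** The fixed direction applies to counts. SAP 4.4 allows non-missing denominators, so a participant with only normal unscheduled values would enlarge the denominator under the new rule, and a percentage could fall slightly. This stands as a qualification.
- **Part A size.** The total of 90 to 105 uses the Part A design target. The only enrolment count given is 15 at 31 January 2019 (protocol section 2). With 15, N = 80 and 1/N = 1.25 points, which changes nothing of substance.
- **Weight.** There is no comparator, test or decision rule on these tables, and SAP section 4 permits extra tables in the CSR. This limits the importance but leaves the stated rule unsuitable for these outputs.

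**Conclusion.** The concern holds. As written, 4.3.7 is the wrong rule for the minimum and maximum shift tables, the liver CTCAE incidence and the Hy's law count. For counts, any error can only make the results look more favourable.

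The size is unknown and could be zero, because it depends on how many participants have their worst value only in an unscheduled or repeat sample. Where that happens, the 1/N steps above apply, given the planned sizes and a post-baseline value for everyone. In the small cohorts a single participant is visible.

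The point is limited to supportive laboratory tables. The endpoint of AE frequency, duration and severity is not directly affected, and the by-visit summaries are sound. It should be fixed because safety is the study's only objective and the correction is simple.

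**What to change.** Make two changes to the SAP:

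1. In 4.3.7, limit the scheduled-only rule to by-visit descriptive summaries.
2. In 4.17, state that the minimum and maximum shift tables, the ALT, AST, ALP and total bilirubin CTCAE incidence, and the Hy's law count use all post-baseline values: scheduled, unscheduled and repeat. For the combined ALT and bilirubin criterion, pair unscheduled values by the same collection date.

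It would help to name the denominator for these outputs in the same sentence, for example participants with at least one post-baseline value of the test.

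The cost is about one sentence in each section and minor reprogramming of three outputs. No visits, samples or data are added, since 4.3.7 already commits to listing these values, and the by-visit tables do not change. The one drawback is that laboratory incidences may look slightly less favourable.
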